14.1.2. Assessment of peers as part of Component C

Peers will call the study or carry out the assessment independently in REDCap. The peer coupon includes a QR code that brings peers to the peer assessment as well as the study phone number.

If the peer is interviewed by a staff member, peers will provide verbal informed consent following an IRB approved form and receive a brief interview that includes their coupon number, age, race/ethnicity, sex, occupation, relationship to the participant, true/false questions on the core messages, COVID-19 testing experiences, and COVID-19 vaccination experiences. They will be given referrals to COVID-19 testing and vaccination locations as needed.

If the peer follows the QR code, peers will read the informed consent form in REDCap and indicate their informed consent, then carry out the brief interview.

We will collect some identifying information on the peer (name, email address, mailing address) in order to compensate the peer for the interview and inform the participant educator that the peer contacted the study.

14.1.3. Qualitative interviews

Qualitative interviews will follow a semi-structured interview guide with questions and prompts focused on barriers to and facilitators of COVID-19 testing and vaccination, and regarding acceptability of the intervention components.

14.1.4. COVID-19 self-test kit (with FDA EUA)

The present study does not test participants for COVID-19 but as part of Component D: navigation, half the sample will be provided with rapid antigen self-test kits for COVID-19 that has received U.S. Food and Drug Administration (FDA) emergency use authorization (EUA) or full FDA approval.

We will provide the ACON Biotech Flowflex SARS-CoV-2 Antigen Rapid Test (Self-Testing). We will refer to this as the FlowFlex test.

This test is provided in a white box. (FlowFlex tests in a dark blue box do not have FDA EUA.)

An independent evaluation conducted by the National Institutes of Health's (NIH) RADx program has indicated that the Flowflex™ COVID-19 Antigen Home Test does detect the Omicron variant in live clinical samples (<https://www.aconlabs.com/flowflex-documents-new/>).

14.1.5. Update to Flowflex EUA – serial testing for asymptomatic or symptomatic individuals is required

On June 21, 2022, the FDA updated the Flowflex EUA letter (<https://www.fda.gov/media/152700/download>) to require serial testing for asymptomatic individuals. As it is worded in the EUA, "the test is authorized for individuals with or without symptoms or other epidemiological reasons to suspect COVID-19 when **tested twice over three days with at least 24 hours (and no more than 48 hours) between tests.**"

All RADx-UP projects using Flowflex must modify their testing strategy to ensure participants are informed that “testing” means they are tested twice over three days with at least 24 hours (and no more than 48 hours) between tests.

The present study adherence to FDA guidelines. Study intervention materials and assessment instruments were revised to reflect these changes.

14.2. Primary outcome

The study’s primary outcome is **COVID-19 testing confirmed with documentary evidence** (e.g., a doctor’s note or patient portal electronic health record note [e.g., from MyChart] that includes the type of test, date of testing, and the result, or a photograph of a self-test result).

As of March 16, 2022, the NYC Department of Health and Mental Hygiene recommends the following: “People who have frequent in-person contact with others and are not fully vaccinated should consider getting tested weekly. This is especially true for people in close contact with others who are not wearing masks indoors” (<https://www1.nyc.gov/site/doh/covid/covid-19-testing.page>).

This is consistent with CDC guidelines: “The CDC recommends conducting screening testing of unvaccinated, asymptomatic workers without known or suspected exposures at least weekly (https://www.cdc.gov/coronavirus/2019-ncov/community/organizations/testing-non-healthcare-workplaces.html#anchor_1615914276994).

14.3. Primary outcome definition and evaluation

The study’s primary outcome is at least one instance of diagnostic **COVID-19 testing in the past six weeks (that is, not antibody testing), confirmed with documentary evidence of the result** (e.g., a doctor’s note or patient portal electronic health record note [e.g., from MyChart] that includes the type of test, date of testing, and the result, or a photograph of a self-test result or self-test results).

The present study does not test participants for COVID-19. Instead, the present study tests a number of intervention components intended to increase regular COVID-19 testing in this population. Participants can receive testing at any community site or carry out home testing.

The present study does provide half of the participants with FlowFlex test **kits** as part of Component D: navigation. Thus, we expect that many participants will use the FlowFlex test. (We provide two test kits in the self-test level of Component D. Starting in January of 2023, we inform participants in the self-test level of Component D that three tests are recommended in certain circumstances. We provide information on how to obtain tests.)

Many self-tests require serial testing within a proscribed window of time **in certain circumstances** (e.g., BinaxNOW, Nano-Check, INDICAID, Inteliswab, **Flowflex**), while other tests require a single test. Tests with current EUAs are listed here: <https://www.fda.gov/medical-devices/coronavirus-disease-2019-covid-19-emergency-use-authorizations-medical-devices/in-vitro-diagnostics-euas-antigen-diagnostic-tests-sars-cov-2>

The number of rapid tests required for a complete test for several of the serial rapid test kits has changed during the pandemic, including the test we use in the project (Flowflex). This makes assessing rapid test completion complicated. **Thus, we will define an “instance” of COVID testing as any single time a COVID test was administered, whether a rapid, PCR, or other type of test.**

We will also assess test COMPLETION as a secondary outcome. Test completion is defined below.

Thus, we will assess “instances” of testing for COVID-19 at follow-up and for each instance will assess:

- Main reason for testing (e.g., screening testing/asymptomatic, exposure, upcoming travel, return from travel, preparing for upcoming event, work requirement, symptomatic, other) over the prior 6 weeks.
- Mechanism of test: Self-test (rapid) or self-test collection vs. facility-based testing
- Type of COVID-19 test (rapid/antigen, PCR/molecular)
- If self-test, brand name of self-test (e.g., FlowFlex, Inteliswab, BinaxNOW, etc). Participants can send a photograph of the test kit box to aid in determining which test was conducted.
- Number of self-tests required in this instance
- Number of self-tests carried out in this instance
- If serial testing was carried out, number of hours between the first and second test
- If facility-based testing was carried out, location of testing (laboratory, a standalone testing site, a doctor's office or health clinic, hospital, other)
- Dates of test(s)
- Result of test(s) – positive, negative, inconclusive, unknown

We will code these data regarding COVID testing behavior in the following manner:

- For non-serial test kits: testing was PERFORMED COMPLETELY if one self-test was completed
- For serial test kits that require two tests within a certain window of time (e.g., Flowflex until December of 2022, BinaxNOW), testing was PERFORMED COMPLETELY if two tests were carried out in compliance with the package instructions. If one test was completed, and no PCR test was completed, we will code the test as PERFORMED INCOMPLETELY
- For serial test kits that require three tests within a certain window of time (e.g., Flowflex after December of 2022), testing was PERFORMED COMPLETELY if three tests were carried out in compliance with the package instructions. If one or two tests were completed, and no PCR test was completed, we will code the test as PERFORMED INCOMPLETELY
- For serial test kits, if participants receive one self-test followed by a PCR test, testing will be coded as PERFORMED COMPLETELY
- When participants receive a PCR test, testing will be coded as PERFORMED COMPLETELY

We will request documentary evidence for the result of each test. Documentary evidence will be coded as present or absent for each test.

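### Section 14.3 makes three Flowflex tests depend on circumstances, but its completion coding for Flowflex after December 2022 goes by kit and date

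*Combined protocol and SAP*

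**What the plan says.** All of this is in section 14.3 of the combined protocol and SAP unless stated.

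- Completion is a declared outcome: "We will also assess test COMPLETION as a secondary outcome".
- From January 2023, participants in the self-test level of Component D are told "that three tests are recommended in certain circumstances". The same section also says that several self-test brands, Flowflex among them, need serial testing only in some circumstances.
- For each testing instance the study records, among other things, "Main reason for testing (e.g., screening testing/asymptomatic, exposure, upcoming travel" and further reasons, the brand, the dates, the number of self-tests done, and "Number of self-tests required in this instance".
- The coding rules then sort instances by type of kit. Flowflex until December 2022 is an example of a two-test kit. The three-test rule begins "For serial test kits that require three tests within a certain window of time (e.g., Flowflex after December of 2022" and ends "If one or two tests were completed, and no PCR test was completed, we will code the test as PERFORMED INCOMPLETELY".
- For serial kits, "if participants receive one self-test followed by a PCR test, testing will be coded as PERFORMED COMPLETELY". Any PCR test also counts as complete.

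Section 14.1.5 gives the only other Flowflex requirement in the documents. It is the June 2022 authorization wording, under which "the test is authorized for individuals with or without symptoms or other epidemiological reasons to suspect COVID-19" when two tests are done over three days.

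**The concern.** One part of the section makes the three-test number conditional. The coding rule, by its own example, attaches that number to the kit from a calendar date onward. The field that would reconcile the two, the number required in that instance, is collected but not used in any coding rule.

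At stake is the completion outcome. Section 15.5.1 plans logistic models of component effects on secondary outcomes, so completion would be modelled by component. Flowflex is supplied in only one level of Component D, as two kits, and section 14.3 expects many participants to use it. A coding rule that marks some adequate two-test instances as incomplete could therefore fall unevenly across that contrast. Section 12.5.1 shows that eligibility for the optimization trial was still being revised in May 2023, which suggests that some follow-up falls after the coding change.

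**Working it through.** The plan gives no figure to reproduce. The check applies the coding rules as a decision table.

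**Inputs**
- r = number of tests required in the instance (recorded, section 14.3).
- d = number of tests carried out in line with the package instructions (section 14.3).
- Flowflex, after December 2022, no PCR. With a PCR the instance is complete under either rule below.
- r = 3 in the three-test circumstances (section 14.3). Outside them r is below 3. The documents do not say whether it is 2 or 1. Section 14.1.5 points to 2, while the section 14.3 remark that serial testing is needed only in some circumstances leaves 1 open.

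**Rules**
- Kit-and-date reading of section 14.3: complete if d ≥ 3.
- Required-number rule: complete if d ≥ r.
- The two disagree exactly when r ≤ d < 3.

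**Result**

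| Required r | Done d | Kit-and-date | Required-number | Agree? |
|---|---|---|---|---|
| 3 | 1 | incomplete | incomplete | yes |
| 3 | 2 | incomplete | incomplete | yes |
| 3 | 3 | complete | complete | yes |
| 2 | 1 | incomplete | incomplete | yes |
| 2 | 2 | incomplete | complete | **no** |
| 2 | 3 | complete | complete | yes |

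If r were 1, two tests done would still meet the requirement (2 ≥ 1) and would still be coded incomplete (2 < 3). The finding for d = 2 therefore does not depend on whether the number outside the three-test circumstances is 1 or 2. A single test done (d = 1) would be miscoded only if r = 1, which the documents do not establish.

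**Direction.** Whenever d ≥ 3, d ≥ r also holds for every r up to 3. The kit-and-date reading never codes an inadequate instance as complete, so any error is towards incomplete.

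**Earlier period.** Until December 2022 the rule for Flowflex is complete if d ≥ 2, which matches the two tests of section 14.1.5. With r = 2 and d = 1, 2 or 3 there is no disagreement.

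The rows are logical possibilities, not a rate. The documents do not report how many instances fall in any row, and they do not define a participant-level completion variable.

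**The case against.** The strongest reply is that the three-test rule defines its class as kits that require three tests and gives Flowflex only as an example. The rules are introduced as applying to the recorded data, which include the required number, and both serial rules refer to the package instructions. A coder could therefore place a two-test instance under the two-test rule and code it correctly. This stands in part. It means one cannot say that the plan treats every Flowflex instance after December 2022 as needing three tests. It does not settle the matter, because the example sorts Flowflex by date alone and no rule points to the required-number field. Two coders could code the same instance differently.

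A second reply is that no text states that any Flowflex instance after December 2022 required two tests. That is true: the number is an inference from sections 14.1.5 and 14.3. It does not remove the conflict, since two tests suffice wherever three are not required. It does mean that the number of affected instances may be zero, for example if every such instance fell in the three-test circumstances.

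A third reply is that a kit-and-date rule is uniform, whereas a required number reported by participants might not be. This stands, and it shapes the fix. The three-test advice is described only for the self-test level, so what participants believe was required could differ between the levels of Component D.

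A reader might also infer two stronger points. One is that single Flowflex tests are miscoded. The documents do not show that one test was ever enough. The other is that the self-test level is biased downward on completion because it receives two kits. Where three tests were required, two are correctly coded as incomplete, participants are told how to obtain more tests, and no counts are available.

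**Conclusion.** Section 14.3 is internally inconsistent on when three Flowflex tests count as complete testing. On the kit-and-date reading that its example suggests, an instance after December 2022, outside the three-test circumstances, with two compliant tests and no PCR, is coded as incomplete although it met its requirement. On the per-instance reading it is coded correctly.

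No size can be given. The count of affected instances may be zero, and the effect on the Component D contrast cannot be derived from the documents. The trial team can bound the two-test case from its own data, as the number of Flowflex instances after December 2022 with exactly two compliant tests and no PCR.

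The conclusion assumes that some instances after December 2022 fell outside the three-test circumstances, as the conditional wording implies.

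The point is minor. The primary outcome counts any single documented test, the optimization decision in section 15.5.1 does not use completion, and completion is not named in the secondary-outcome lists of sections 14.4 and 15.3. The required and completed counts are both recorded, so nothing is lost and the outcome can be recoded.

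**What to change.** In section 14.3, define an instance as complete when the number of self-tests carried out in line with the package instructions is at least the number required in that instance. Specifically:

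1. Staff set the required number by one rule for all participants, from brand, test date and main reason for testing, under the package instructions in force on that date. It should not rest on participant report alone. The protocol does not define the three-test circumstances, so they must be written down from those instructions.
2. Keep the existing rules for PCR and for a self-test followed by PCR.
3. When the required number cannot be verified, use the kit-and-date number as the default.
4. Report the kit-and-date coding as a sensitivity analysis.

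The cost is one or two sentences in section 14.3, a short staff check, a recode from fields already collected and one sensitivity table. Some uncertainty in the required number will remain, which the common rule and the default limit but do not remove.

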14.4. Secondary outcome evaluation

Secondary outcomes include:

- Result of each COVID test
- If diagnosed with or has a positive COVID test result
 - confirmatory testing, as needed (PCR testing is recommended for symptomatic negative and asymptomatic positive persons who carry out a rapid test)
 - contact tracing
 - self-isolation
 - health care receipt
 - unintended consequences

For all participants:

- attitudes toward COVID-19 vaccination
- receipt of COVID-19 vaccination (the CDC vaccination card will be shown if possible)

These primary and secondary outcomes will be examined in mixed methods and integrated analyses.

15. Statistical Considerations

15.1. Sample size, precision, and statistical power

For the primary outcome, COVID-19 testing by the final follow-up, we used PASS 2021¹³⁹ to estimate the sample size needed for individual main effects of intervention components corresponding to odds ratios of 2.0 in logistic regression, given $\alpha=.05$. Assuming participants not receiving or receiving the lowest intensity of each component have a 20% chance of testing by the final follow-up, a sample size of n=352 (n=22 in each of 16 conditions) provides 80% power to detect an odds ratio of 2.0 (i.e., 20% vs. 33% tested). To account for attrition of up to 20% of enrolled participants, we propose a total sample size of 448 participants (n=28 in each of 16 conditions), ensuring complete data for at least n=22 per condition. Given the proposed sample size, when the main effect of an intervention component on a continuous measure of a secondary outcome or mediator is estimated in a linear model or independent-samples t-test, the sample size provides 80% power to detect a small standardized mean difference ($d = .30$). Moderator effects corresponding to an odds ratio of OR=1 in one subgroup and OR=4 in another can be detected with 83% power if subgroups sizes are roughly equal. To estimate the size of a mediated effect that can be detected given the proposed sample size, we use the approach described by Vittinghoff and colleagues¹⁴⁰ as implemented in PASS 2021. Given a substantial correlation between an intervention component and a hypothesized mediator ($r=.50$), an odds ratio of 1.50 can be detected with >80% power for the effect of a one-SD increase in a continuous mediator on the COVID-19 testing outcome, controlling for treatment assigned.

15.1.1. Missing data

Missing data in longitudinal studies are inevitable despite best efforts at retention. Several procedures based on differing assumptions about the randomness of the missing data will be implemented¹⁵⁷. Missing values may be handled by full information maximum likelihood (FIML)^{158,159}. Inverse probability weighting^{160,161} and multiple imputation¹⁶² will be considered as well. These approaches to handling missing data assume data are missing at random (MAR). In addition, methods for non-ignorable missing data (missing not at random; MNAR) such as Heckman's selection model^{158,163} and pattern-mixture models^{162,164,165} will be used. Sensitivity analyses will assess the degree to which results depend on untestable assumptions.

15.2. Primary endpoint/outcome

The primary outcome is at least one instance of COVID-19 testing in the past 6 weeks, with documentary evidence of the testing.

15.3. Secondary endpoints/outcomes

Secondary outcomes include:

- Result of each COVID test
- If diagnosed with or has a positive COVID test result
 - confirmatory and re-testing (as needed)
 - contact tracing
 - self-isolation
 - health care receipt
 - unintended consequences
- attitudes toward COVID-19 vaccination
- receipt of COVID-19 vaccination

These primary and secondary outcomes will be examined in mixed methods and integrated analyses.

15.4. Data Transfer Agreement (DTA) Security Level

As per our Notice of Award, data will be transmitted to the RADx-UP Coordination and Data Collection Center (CDCC) weekly.

Our data security level is LIMITED.

We will not provide: Names, street address (city, county, state, and zip code are allowed), Telephone / Fax numbers , email, Medical record numbers, Health plan beneficiary numbers.

This corresponds to the following Common Data Elements (CDEs): first_name, last_name, current_street, current_street2, mobile_phone, home_phone, other_phone, personal_email, other_email, mrn

All other data including the Tier 1 CDEs will be transmitted to the CDCC on the schedule determined by the CDCC (e.g., quarterly).

15.5. Statistical methods

15.5.1. Quantitative data analysis

Intent-to-treat analysis will be our primary analytic approach and exploratory analyses will examine complier average effects of intervention components^{124,125}. Approaches to missing data will include full information maximum likelihood estimation¹²⁶ and multiple imputation¹²⁷. In sensitivity analysis, missing data will be treated as failure to achieve the desired outcome. If data are missing not at random (MNAR), we will employ sensitivity analysis, using selection¹²⁸ or pattern mixture^{129,130} models.

Aim 1: Identify which of four components or interactions between components contribute meaningfully to improvement in the primary outcome, COVID-19 testing with documentary evidence, and from these results, optimize a multicomponent intervention.

The primary outcome for Aim 1 is COVID-19 testing with documentary evidence by the final follow-up point (12-weeks post-baseline). Logistic regression will be used to estimate effects of components on the odds of COVID-19 testing. Intervention components will be effect-coded to estimate main effects, two-way, three-way, and four-way interactions of all four components (see **Equation 1**). The coefficient for an effect-coded main effect term (e.g., b_1), multiplied by two and exponentiated, will estimate the effect of the component (e.g., Component A) on the odds of testing. Similarly, the coefficient for an effect-coded interaction term, multiplied by two and exponentiated, will estimate interaction effects between or among components on the odds of testing. Similar logistic regression analyses will estimate effects of components on secondary outcomes.

Equation 1

Intervention optimization. Based on main and interactive effects estimated in Aim 1, we will use a decision-making process to select the most effective combination of component levels, eliminating ineffective or poorly performing components. The decision-making process will be led by Drs. [name], [name], [name], [name], and [name] and using procedures outlined in Collins⁴⁸. To identify

important component main effects, we consider both statistical significance at $p < .05$ as well as the probability the more effective component level multiplies the odds of testing by at least $OR = 1.2$. This effect size threshold is based on the idea that several components with an effect as large or larger would comprise a potent multicomponent intervention. We will use a Bayesian generalized linear model with non-informative priors to calculate the probability of $OR \geq 1.2$ from the posterior distribution.

Component main effects that are statistically significant ($p < .05$) and have a probability $> .5$ of $OR \geq 1.2$ will be considered important and placed into a screened-in set. Membership in the screened-in set will be reconsidered in light of any important interactions. Interactions that are statistically significant ($p < .05$) and have a probability $> .5$ of $OR \geq 1.2$ will be considered important. For example, a component level that does not meet criteria for an important main effect could be included if it enhances the effectiveness of another component. Component levels that make up the optimized intervention are comprised of the higher levels from the screened-in set and the lower levels from the screened-out set.

Aim 2: Identify mediators and moderators of the efficacy of each intervention component. To examine potential mediating mechanisms, analysis for **Aim 2** will use the potential outcomes framework¹³²⁻¹³⁴. This framework highlights assumptions needed to identify direct and indirect effects of interest: no unmeasured cofounders of the exposure (an intervention component) and outcome (COVID-19 testing) relation; no unmeasured confounders of the mediator and outcome relation; no unmeasured confounders of the exposure and mediator relation; and no measured or unmeasured confounders of the mediator and outcome relation affected by exposure. Since intervention components are randomly assigned, the key issue for the proposed study is addressing confounding of the relation between mediators and outcomes. Mediators measured at baseline will be included as confounders of the relation between follow-up mediators and COVID-19 testing by the final follow-up. Because unmeasured confounding of relations between mediators and outcomes may remain despite attempts to measure and include known confounders in the models, sensitivity analysis will be undertaken to determine how the size of the correlation between error for the mediator model and error for the outcome model impacts inferences for direct and indirect effects. The total natural indirect effect (TNIE) and pure natural direct effect (PNDE) of each component will be estimated using the *mediation* R package¹³⁵. The TNIE compares the outcome when subjects are exposed (e.g., receive a component), and the mediator varies as it would naturally under exposure, versus the outcome when subjects are exposed but the mediator varies as it would naturally in the absence of exposure (i.e., component not received). In other words, the difference estimated by the TNIE compares the expected outcome when the intervention has its natural impact on the mediator versus the expected outcome when the action of the mediator is blocked. The PDNE compares participants at different levels of a component (e.g., On vs. Off) when a mediator is blocked.

Potential moderator effects will be examined by adding interaction terms to the model described for **Aim 1**. We will include sociodemographics (e.g., age) and occupation as covariates and explore the interactions of these variables with intervention components. When interaction effects are detected, we will estimate the simple main effects of the intervention component across levels of the moderator variable (e.g., MI counseling effects on testing for younger vs. older participants). Identified moderators will inform future adaptive interventions¹³⁸.

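### The 80% power is for a single two-group comparison, but components are screened on p-values from a 16-term logistic model that does not reliably deliver it

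*Combined protocol and SAP*

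**What the plan says.** Section 15.1 plans for individual component main effects with an odds ratio of 2.0 at a 5% significance level: "a sample size of n=352 (n=22 in each of 16 conditions) provides 80% power to detect an odds ratio of 2.0". The base rate is introduced with "Assuming participants not receiving or receiving the lowest intensity of each component have a 20% chance of testing by the final follow-up". Enrolment is raised to 448 (28 per condition) for attrition of up to 20%, "ensuring complete data for at least n=22 per condition".

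Section 15.5.1 (Aim 1) uses logistic regression: "Intervention components will be effect-coded to estimate main effects, two-way, three-way, and four-way interactions of all four components". A component's odds ratio is its effect-coded coefficient, doubled and exponentiated. Main effects with p < .05 and a posterior probability above .5 of an odds ratio of at least 1.2 "will be considered important and placed into a screened-in set". Membership is then reconsidered in the light of interactions.

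The documents do not say whether the test is Wald or likelihood-ratio. They give no rule for a condition in which nobody, or everybody, was tested, and no model with fewer terms for the main effects.

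**The concern.** In a balanced linear factorial model, interaction terms are orthogonal to the main effects and cost them almost nothing. That does not carry over to logistic regression. With all interactions fitted, each main effect is an equal-weighted contrast of 16 condition-level log-odds, so the conditions with the fewest events dominate its variance. A condition with no events makes the ordinary estimate infinite and its Wald test useless.

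The power statement allows for neither effect. The main-effect p-value is one of the two criteria for screening a component in. At stake is whether a component that works is left out of the optimized package or, with a likelihood-ratio test, whether an inactive one meets the p-value criterion too often.

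**Working it through.** **Inputs.** From 15.1: 20% against 33% (odds ratio 2.0), significance level .05 (taken as two-sided, which reproduces the stated figure), 352 people with complete data, 22 per condition. From 15.5.1: all interactions fitted. My assumptions: every other active component also has an odds ratio of 2.0, and there are no true interactions on the logit scale.

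**1. The plan's figure.** Two groups of 176:

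SE² = 1/(176 × 0.20 × 0.80) + 1/(176 × 0.333 × 0.667) = 0.0355 + 0.0256 = 0.0611, so SE = 0.247.

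ln 2 / SE = 0.693/0.247 = 2.805. Power = Φ(2.805 − 1.960) = 80.1%. The stated 80% is reproduced with no allowance for other components.

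**2. The planned model.** It has 1 + 4 + 6 + 4 + 1 = 16 terms for 16 conditions. For Component A:

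Var(2b₁) = (1/64) × Σ 1/[22 p(1 − p)], summed over the 16 conditions.

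- Only A active: (1/64) × [8/3.52 + 8/4.89] = 0.0611, as in step 1.
- All four active, A-off conditions averaging 20%: the rates are 7.4% (one condition), 13.7% (four), 24.2% (six), 38.9% (four) and 56.0% (one). Σ 1/[p(1 − p)] ≈ 14.6 + 33.7 + 32.7 + 16.8 + 4.1 ≈ 102. The variance is 102/(22 × 64) = 0.0724, so SE = 0.269 and power = Φ(0.693/0.269 − 1.960) ≈ 73%. The same large-sample calculation for the main-effects model gives 77%.

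**3. Empty or full conditions.** The chance of at least one is 1 − Π[1 − (1 − p)²² − p²²]. This is 5.9% with only A active and 31.4% with all four active. In such trials the ordinary Wald test cannot reject; one example fit gave a standard error of about 1,059.

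**4. Simulation.** 22 per condition, A-off average 20%, 10,000 to 20,000 trials per scenario. An ordinary Wald fit with an empty or full condition counts as no rejection.

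| Power for A (%), by number of active components including A | 1 | 2 | 3 | 4 |
|---|---|---|---|---|
| 16-term, ordinary Wald | 76 | 67 | 57 | 48 |
| 16-term, penalised Wald | 80 | 76 | 74 | 71 |
| 16-term, likelihood ratio | 81 | 80 | 77 | 73 |
| Four main effects, Wald | 81 | 80 | 79 | 78 |

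Size for an inactive component, with none to three others active:

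- 16-term, ordinary Wald: falls from about 4.2% to 1.3%.
- 16-term, penalised Wald: about 3% with three others active.
- 16-term, likelihood ratio: 7.4% to 8.1%.
- Main-effects model: about 5% throughout.

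Enrolling 448 with random 20% loss gives the same picture. With all four active, ordinary Wald power is 47.6% and main-effects power 78.8%.

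**5. Sensitivity.**

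- With three other components at odds ratio 1.5, penalised Wald power is 77% against 80% for main effects. At 1.2 it is 80% against 82%.
- If 20% is the rate in the lowest condition and at least one other component works, the 16-term model has at least about 83% power. Ordinary Wald size is about 5% and likelihood-ratio size 6.1-6.5%.

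**6. The 22 per condition.** At 20% independent loss, P(Bin(28, 0.8) ≥ 22) = 0.678, and 0.678¹⁶ = 0.2% for all 16 conditions. At 15% loss it is 0.885¹⁶ = 14%, and at 10% loss 0.982¹⁶ = 75%. The expected total at 20% loss is 448 × 0.8 = 358, and the chance of at least 352 in total is 79%.

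**The case against.** The strongest reply is that the shortfall depends on choices the documents leave open.

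- **The base rate.** The wording on the 20% can be read as the condition with every component at its lowest level, and then the 16-term model is adequate once another component works. That reading is possible. But the arithmetic in 15.1 compares two margins, and section 9 describes a main effect as eight conditions against eight, so the off-level average fits better.
- **The scenario.** Odds ratios of 2.0 for all four components are the extreme case. Section 4.3 gives one or two components as an example of the optimized package. This stands, and the gap does narrow with weaker effects. Even so, with two active components ordinary Wald power is about 67%.
- **The cause.** With four active components, penalising alone lifts Wald power from 48% to 71%; moving to main effects adds about 7 points. Under the ordinary Wald test, empty conditions are therefore most of the problem. This stands, and the fix needs an empty-cell rule.
- **Other models.** A model with main effects and two-way interactions also holds its size, with about 75-82% power, so the three- and four-way terms do most of the harm.
- **The decision rule.** The p-value is not the only criterion: the posterior probability counts too, and interactions can change the set.
- **Attrition.** Loss below 20%, or multiple imputation, would ease the cell-size point.

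A reader might infer that the planned model fails on both level and power, or that the trial is too small. The documents do not support either. The Wald tests miss 5% only on the conservative side. The likelihood-ratio test exceeds 5%, but keeps about 80% power with one or two active components. The sample size of 352 is right for the comparison it describes. Nor does the problem need other active components: with only one active, ordinary Wald power is already about 76%.

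**Conclusion.** The point holds in this form: the stated 80% is a property of a one-component comparison, not of the model that supplies the screening p-value. With 20% as the off-level average and odds ratios of 2.0, power in the 16-term model falls from 76% to 48% (ordinary Wald), 80% to 71% (penalised Wald) or 81% to 73% (likelihood ratio) as the number of active components rises from one to four. The likelihood-ratio test also has size of 7-8%. A main-effects model stays at about 78-81% power with size near 5%; it does not restore exactly 80% in every scenario.

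The size of the other effects is an assumption, and the base-rate reading is an inference from the plan's own arithmetic. Separately, 28 per condition does not ensure 22 with complete data in each condition at 20% loss.

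**What to change.** **Section 15.5.1.** Take the main-effect estimates, p-values and posterior probabilities used for screening from the logistic model with the four main effects. Use the model with interactions to screen interactions. Name the test, and specify a penalised fit (for example Firth) for empty or full conditions. Report the equal-weighted main effect from the interaction model alongside.

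**Section 15.1.** State that the 80% (about 78-81% under the scenarios above) refers to the main-effects model, and that 20% is the average over the conditions without the component. Replace the assurance of at least 22 per condition with: about 22 per condition on average (about 358 in total) at 20% attrition.

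If main effects stay in the 16-term model, restate power for the named test: about 48-76% for ordinary Wald, 71-80% for penalised Wald, or 73-81% for likelihood ratio with size of 7-8%.

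**Cost.** The change is to the analysis text only; sample size and conduct are unaffected. The downside is a change of estimand if interactions are real: the main-effects estimate is then a precision-weighted, not equal-weighted, average over the other components. That is why both should be reported.
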